#### Master Clinical Protocol 2018-10

colonoscopy will be excluded from all analyses. Subjects with unevaluable Exact CRC screening test results will be excluded from the primary endpoint analyses. All excluded cases will be assessed for bias.

Subjects with colonoscopic/histopathologic findings in category 1 (confirmed colorectal cancer cases) will be considered to have a positive outcome and will be included in the CRC sensitivity calculations. Note: Due to the low prevalence of CRC in the Age 45-49 group, there will likely be no CRC prospectively enrolled in the study, so no endpoints will be designed around CRC sensitivity. Similarly, due to the low prevalence of AA in the Age 45-49 group there may only be approximately 29 subjects\* with colonoscopic/histopathologic findings in category 2 (advanced adenomas) prospectively enrolled in the study, so no endpoints will be designed around AA sensitivity.

\*Advanced adenoma prevalence among never-screened individuals aged 45-49 years may be derived, based on simulation results, to be 3.92%. 731\*3.92%= 29 [9].

#### 12.3 Sample Size and Rule Out Lower Threshold Justification

The minimum number of non-advanced neoplasia and negative instances (categories 3-6.2) needed to rule out an 85.0% lower bound on the specificity with 90% power for a one-sided test with 2.5% Type 1 error according to an exact binomial distribution is 225, as outlined in Table 1. Furthermore, the minimum sample size needed such that the confidence interval width for the alternative proportion (92.2%) is within +/-2.2% (i.e. 92.2%+/-2.2% = 90.0%/94.4%) is 731. Using this sample size, the power of the study is >99.99%.

Table 1: One-sided Exact Test Power: Single Proportion

Sample Size Scenarios	1	2
Test significance level, α	0.025	0.025
One or 2-sided test	1	1
Null hypothesis proportion	85.0%	85.0%
Alternative Proportion	92.2%	92.2%
Power (%)	90%	>99.99%
# Non-CRC/AA Cases	225	731

The alternative proportion of 92.2% is the observed specificity in the DeeP-C study [SSED P130017, Source: fda.gov] for the age group 50-59. It is anticipated that the specificity of Cologuard in individuals age 45-49 is not different than the specificity of the next closest age category. The null hypothesis proportion of 85.0% is identical to specificity null hypothesis used in the DeeP-C study (NCT).

A minimum sample size of 193 evaluable subjects (age 45-49 inclusive) is required to adequately power the primary analysis. This minimum sample size requirement will be adjusted to 731 to more accurately estimate the specificity by narrowing the CI. Since the expected drop-out rate is 20%, the total enrollment target is 914 (i.e. 731/ (0.8) = 914).

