#### 9.4 Subject Replacement

Enrolled subjects may be replaced for any of the following reasons:

- 1. No stool sample provided and/or no completed colonoscopy procedure.
- 2. A valid stool sample result cannot be obtained for a subject after two (2) attempts (Section 10.4).

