#### 10.8 End of Study

Subjects will be considered completed from the study when they have provided a stool sample and have completed their colonoscopy procedure, OR at the point of subject withdrawal per Section 9.3.

Ensure all data is assessed, entered into the CRF and reporting on AEs/SAEs, UADEs, and/or Protocol Deviations has occurred, if necessary.

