#### 12 DATA ANALYSIS AND STATISTICAL METHODS

Detailed methodology for summary and statistical analyses of the data collected in this study will be documented in a Statistical Analysis Plan. This document may modify the plans outlined in the protocol; however, any major modifications of the primary endpoint definition and/or its analysis will also be reflected in a protocol amendment.

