#### 16 A DEFINITION OF END TRIAL

End of Trial is defined when 731 subjects have completed required study procedures with complete data receipt or on the date of early termination notice.

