### 2.7.2 Subject Replacement Rules

Subjects who are withdrawn due to no stool sample provided within 30 days of enrollment or due to colonoscopy procedure not done may be replaced.

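### 731 is defined as category 3-6 subjects, but the 914 target and the end-of-trial rule allow nothing for advanced neoplasia; the second minimum of 193 and the random-sample wording also need correcting

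*Protocol*

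**What the plan says.** Protocol 12.3 sizes the study in subjects without colorectal cancer or advanced adenoma, that is, categories 3 to 6. Table 1 counts both of its scenarios, 225 and 731, in that unit. The 225 is the minimum for 90% power in an exact one-sided 2.5% test of 85.0% against 92.2%. The 731 is the minimum for an interval within 2.2 points of 92.2%. SAP 2.2 gives 731 in the same unit. Protocol 12.3 then adds two statements:

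- a second minimum: "A minimum sample size of 193 evaluable subjects (age 45-49 inclusive) is required to adequately power the primary analysis";
- the enrolment target: "Since the expected drop-out rate is 20%, the total enrollment target is 914 (i.e. 731/ (0.8) = 914".

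The footnote to Protocol 12.2, repeated in SAP 2.8.1, says that advanced-adenoma prevalence "may be derived, based on simulation results, to be 3.92" per cent, and multiplies it by 731 to expect 29 such subjects. SAP 2.2 sets a maximum enrolment of about 942 and attributes it to discontinuation.

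On ending the study, Protocol 16 says "End of Trial is defined when 731 subjects have completed required study procedures", and Protocol 10.8 says "Subjects will be considered completed from the study when they have provided a stool sample and have completed their colonoscopy procedure". Lesion category plays no part in either. SAP 2.9.2 instead ends the study once every subject has completed or discontinued.

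On replacement, Protocol 9.4 says "Enrolled subjects may be replaced for any of the following reasons" and lists a missing stool sample or colonoscopy, and no valid result after two attempts. SAP 2.7.2 says that subjects withdrawn for want of a stool sample within 30 days or "due to colonoscopy procedure not done may be replaced".

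On the analysis set, Protocol 12.3.1 assesses specificity in a random sample of 731, and SAP 2.8.1 in one of approximately 731. Protocol 12.5 bases the primary analysis on all available data, and SAP 2.9.1 uses all subjects where it can.

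**The concern.** One number is used in two units. In Table 1 and SAP 2.2, 731 excludes advanced neoplasia. In the 12.2 footnote, which takes 29 advanced adenomas out of 731, and in Protocol 16, it is everyone who was evaluable or who completed. The step from 731 to 914 removes drop-outs but not the subjects who complete and then fall in category 1 or 2, and those subjects do not enter the specificity denominator.

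Three smaller inconsistencies sit beside this. The same section gives two minima for one test. The two documents end the study on different conditions. The random-sample wording leaves the primary denominator open if more than 731 eligible subjects accrue. These passages fix the sample-size basis, the end of trial and the primary denominator, so they should agree.

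**Working it through.** **Inputs.** Null 85.0%, alternative 92.2%, one-sided 2.5%, 20% drop-out (all Protocol 12.3); advanced-adenoma prevalence 3.92% (Protocol 12.2 footnote); cancers taken as zero, since the plan expects none.

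**1. The plan's own figures.**
- 731 / 0.8 = 913.75, which rounds up to 914. This reproduces.
- Exact test at n = 225: success needs at least 202 negatives, type I error 2.37%, power 92.6%. At n = 224 power is 89.2%. From 225 upward it stays at or above 90% (checked to 499). So 225 reproduces.
- n = 731: success needs at least 641; power 99.999%. The Clopper-Pearson 95% interval at 92.2% is 90.01% to 94.04%, a lower distance of 2.19 points. The first n with a lower distance of at most 2.2 points is 724, so 731 meets the criterion.

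**2. The second minimum.** At n = 193 success needs at least 174; type I error 2.39%, power 88.1%. No variant tried at 90% power gave 193 (exact, normal approximation, continuity correction, one-sided 5%).

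**3. Expected category 3-6 yield.** Yield = enrolled × (1 − drop-out) × (1 − prevalence), without replacement:
- 914 × 0.80 × 0.9608 = 702.5
- 942 × 0.80 × 0.9608 = 724.1

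Under the Protocol 16 rule, drop-out and replacement no longer matter, because the count is of completers: 731 × 0.9608 = 702.3.

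For reference, an expected 731 corresponds to 731 / (0.80 × 0.9608) = 951.03 enrolments.

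**4. What the shortfall costs.**

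| Category 3-6 subjects | Clopper-Pearson 95% at 92.2% | Lower distance (points) | Power against 85% |
|---|---|---|---|
| 702 | 89.96% to 94.07% | 2.24 | 99.998% |
| 724 | 90.00% to 94.05% | 2.20 (2.199) | 99.999% |
| 731 | 90.01% to 94.04% | 2.19 | 99.999% |

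**5. Range.** Assuming drop-out of 15% to 25% and advanced-neoplasia prevalence of 2% to 6% (my ranges, not the plan's), the yield without replacement runs from 761 down to 644 at 914 and from 785 down to 664 at 942. Power at 644 is still 99.995%.

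**6. When the random-sample wording would bite.** More than 731 are expected only if drop-out is below 1 − 731/(914 × 0.9608) = 16.8%, or below 1 − 731/(942 × 0.9608) = 19.2%.

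**The case against.** The best case for the plan has four parts.

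*Replacement and the SAP maximum close the gap.* Replacement is permitted, so 702 is not the plan's stated expectation at 914. Protocol 12 also says of the SAP "This document may modify the plans outlined in the protocol", so a maximum of 942 beside a target of 914 is no contradiction. At 942 the yield is about 724 even without replacement, and the precision criterion is met. The figure may already contain an advanced-adenoma allowance: 731/0.8 + 731 × 0.0392 = 913.75 + 28.66 = 942.4. Most of this stands. That derivation is only an inference, however. SAP 2.2 credits discontinuation alone, and SAP 4.1 refers for justification to Protocol 12.3, where 942 does not appear. Neither document says whether 914 or 942 includes replacements, and advanced neoplasia is not a ground for replacement. Nothing here rescues Protocol 16, which gives about 702 even with full replacement.

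*The 193 is harmless.* The sentence says only that power is adequate, gives no percentage, and is superseded at once by 731. That stands, so a reader should not infer that the plan claims 90% power at 193. It remains a second minimum for the same test, and the only power the section states for a minimum is 90%.

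*The random sample is loose wording* for the usual binomial assumption. That is plausible: the SAP says approximately, and the rest of both documents uses all data. A reader might infer that the sponsor plans to discard evaluable subjects; the documents do not support that. The wording still needs to say what is meant.

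*The inputs are soft.* The drop-out rate is a round planning figure and the prevalence comes from simulation. That also stands, and is why the range is shown.

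**Conclusion.** The passages are wrong as written. This is a minor error of internal consistency: the division 731/0.8 is itself correct, but it is applied to the wrong unit.

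- Protocol 16 stops about 29 short of 731 category 3-6 subjects (731 − 702), with or without replacement. This assumes 3.92% prevalence, no cancers, and that every completer is otherwise evaluable.
- At 914 the same shortfall holds only if non-completers are not replaced. At 942, on that condition, it is about 7 (731 − 724).
- The precision criterion is missed by 0.04 points at 702 and met at 724.
- The 193 has exact power of 88.1%, against 92.6% at 225. This rests on no drop-out or prevalence assumption.

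A reader might go further and infer that the trial is underpowered or that its conclusion is at risk. The figures do not support that: power against 85% stays above 99.99% at every yield considered.

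**What to change.** 1. **Protocol 12.3.** State that 731 counts evaluable category 3-6 subjects. Cite the SAP maximum of about 942, with its derivation and whether it includes replacements. Give the expected yield and precision, both without replacement: about 702 and 2.24 points at 914; about 724 and 2.20 points at 942. Because the section calls 731 a minimum, show the expected yield openly beside it rather than relabelling 731.
2. **Protocol 16.** Bring it into line with SAP 2.9.2, so that the trial ends when all enrolled subjects, up to the stated maximum, have completed or discontinued, and not at 731 completers of any category.
3. **Protocol 12.3.** Delete 193 and keep 225.
4. **Protocol 12.3.1 and SAP 2.8.1.** Replace the random sample of 731 with all evaluable category 3-6 subjects in the ITS population, which SAP 2.2 and 2.6.2 make the effectiveness set, with PP as confirmation. The set has to be named because Protocol 12.2 and SAP 2.8.1 differ on which analyses exclude subjects without documented cecal intubation.

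The cost is a wording amendment to both documents. No enrolment beyond the SAP maximum, and no added visits or assays, are proposed. The price is a stated expected yield slightly below 731.

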#### 12.3.1 Analysis Approach, Primary Effectiveness Analysis

Primary Effectiveness Analysis:

#### Master Clinical Protocol 2018-10

The primary analysis for mt-sDNA test (Cologuard) specificity will be performed using an exact binomial (Clopper-Pearson) test to compute the one-sided 97.5% lower bound; the lower bound must exceed 85.0%. Specificity will be assessed for a random sample of 731 colonoscopy negatives. Rejecting the null hypothesis will demonstrate the Specificity in the Age 45-49 group is no worse than the pre-specified lower bound limit established in the DeeP-C protocol.

#### 12.4 Other Prespecified Analyses

- Analysis of distribution of test performance by race/ethnicity using chi-square tests.
- Analysis of distribution of test performance by age (yearly interval, 45-49) using chi-square tests.
- Analysis of test performance by gender using chi-square tests.
- Analysis of test performance by polyp size and location (including those with no polyps). This
  model will be repeated to include gender, race, and age. Modeling will be regression-based.
- Analysis of Sensitivity to Advance Adenoma (Clopper-Pearson Exact confidence interval). Due to the expected low frequency of Advanced Adenoma, subgroup (Category 2.1, 2.2, 2.3, 2.4) analysis will not be performed, but observed rates will be reported.
- Analysis of Specificity inclusive and exclusive of non-advanced neoplasia (Categories 3.0-5.0)
   (Clopper-Pearson Exact confidence interval).

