#### 12.6.1 Categorical Variables

Categorical variables will be summarized by presenting the number and percent of observations in each category and the two-sided 95% confidence interval (CI), unless otherwise noted. When calculating percentages, the denominator will be the number of participants in the entire study population, unless otherwise specified in the output. Comparisons across Categorical Subgroups will be performed using Chi-Square tests.

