Other Outcome 1:	[REDACTED]
Other Outcome 2:	[REDACTED]

	[REDACTED]
Other Outcome 3:	The rate of no valid mt-sDNA (Cologuard) test result
Other Outcome 4:	[REDACTED]
Other Outcome 5:	[REDACTED]

\*Hypothesis tests will be limited to the primary effectiveness endpoint.

Additionally, baseline demographic information will be presented for all enrolled, and by specificity and sensitivity subsets.

The measures of screening accuracy are defined as follows:

mt-sDNA (Cologuard) Test	Reference Test (Colonoscopy)	
	CRC+	CRC-
sDNA +	A (TP)	B (FP)
sDNA -	C (FN)	D (TN)

Definitions	
Advanced Neoplasia (AN)	Colonoscopic findings that include colorectal cancer (CRC) (category 1) and advanced adenoma (AA) (category 2).
Non-advanced neoplasia (NAN)	Colonoscopic findings $\leq$ 1.0 cm that exclude colorectal cancer (CRC) and advanced adenoma (AA) and include categories 3 – 5.
Sensitivity (Se)	$TP/(TP + FN)$
Specificity (Sp)	$TN/(TN+FP)$
False positive fraction (FPF)	$FP/(TN+FP)$
Odds ratio	$(TP/FP)/(FN/TN)$
Negative likelihood ratio	$(1-Se)/(Sp)$
Positive likelihood ratio	$Se/(1-Sp)$
Negative Predictive Value	$TN/(FN+TN)$ and/or $[Sp*(1-Prevalence)]/[(1-Se)*(Prevalence+Sp*(1-Prevalence))]$ .
Positive Predictive Value	$TP/(TP+FP)$ and/or $(Se*Prevalence)/[Se*Prevalence+(1-Sp)*(1-Prevalence)]$

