## 2.9 Subject Accounting

All subjects will be followed from enrollment to study completion or withdrawal. A correction will be made for the number of subjects lost to follow-up during the study. Age, gender, race, smoking status and ethnicity will be assessed as explanatory covariates in exploratory analyses. These analyses include sensitivity and specificity, negative and positive likelihood ratio (NLR, PLR), and cumulative risk of a false or true positive (cFPR, cTPR). As noted in section 2.8.1, the prevalence of CRC and AA in the study

population is expected to be low, so certain exploratory analyses may not be performed due to this limitation.

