#### **2.10.1 Multiple Comparisons / Multiplicity**

No p-value adjustments will be performed for multiple testing. A p-value will be computed for the primary effectiveness endpoint. The other effectiveness endpoints may include p-values in their evaluation but are considered exploratory endpoints.

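### The exploratory age and race comparisons use chi-square tests alone; adding a trend test for age and exact p-values for sparse race tables would be a cheap improvement

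*Protocol*

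**What the plan says.** Protocol 12.4 lists "Analysis of distribution of test performance by age (yearly interval, 45-49) using chi-square tests" and "Analysis of distribution of test performance by race/ethnicity using chi-square tests", with the same method for gender. Protocol 12.6.1 makes it general: "Comparisons across Categorical Subgroups will be performed using Chi-Square tests". No visible text gives a trend test, an exact test or a rule for small expected counts. SAP section 5 reports no change from the protocol's planned analysis.

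Other text limits the weight of these tests:

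- Protocol 12.4 also plans a model of performance on polyp size and location, and adds: "model will be repeated to include gender, race, and age. Modeling will be regression-based".
- SAP 2.9: "Age, gender, race, smoking status and ethnicity will be assessed as explanatory covariates in exploratory analyses". It also warns that low CRC and adenoma prevalence may rule out some exploratory analyses.
- The footnote to the SAP 2.8.1 endpoint table: "Hypothesis tests will be limited to the primary effectiveness endpoint".
- SAP 2.10.1: "The other effectiveness endpoints may include p-values in their evaluation but are considered exploratory endpoints".

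Most exploratory endpoints in the SAP 2.8.1 table are redacted.

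**The concern.** Age in single years is ordered. If specificity changes steadily across 45 to 49, a general chi-square over five groups spends four degrees of freedom on a one-degree-of-freedom question and loses power.

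The second issue is sparse data. At the planning false-positive rate of 7.8%, a small race group yields very few expected false positives, and the few adenomas are split further by any subgroup. The chi-square approximation can then reject too often or too rarely.

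What is at stake is how well the exploratory subgroup tables can be read: whether a real gradient is noticed, and whether a small p-value by race can be trusted.

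**Working it through.** **The plan's own figures.** No power or sample size is stated for the subgroup tests. The figures in Protocol 12.3 and 12.2 that feed the check reproduce:

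- The stated minimum ("with 90% power for a one-sided test with 2.5% Type 1 error according to an exact binomial distribution is 225") is confirmed for 85.0% against 92.2%. At 225 the rule is at least 202 negatives, with alpha 0.0237 and power 92.6%; from 225 upward power stays at or above 90%.
- At 731, power is 99.999%.
- 731 / 0.8 = 913.75, so 914 enrolled.
- 731 x 3.92% = 28.7, so about 29 adenomas.

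**Inputs.** From the documents: 731 subjects, specificity 92.2% (false-positive rate 7.8%) and about 29 adenomas. Assumed, because the documents give none of these: an even age spread, the race mix and the adenoma sensitivity. Tests are two-sided at 5%.

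**Age, steady gradient.** With n = 731/5 = 146.2 per year and a fall of d per year centred on 92.2%, the deviations are 2d, d, 0, -d, -2d, whose squares sum to 10d². The noncentrality is n x 10d² / [0.922 x 0.078]. For a straight line it is the same for both tests; only the degrees of freedom differ.

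| Fall per year | Noncentrality | 4-df power, formula (simulation) | 1-df trend power, formula (simulation) |
|---|---|---|---|
| 1 point | 146.2 x 0.001 / 0.0719 = 2.03 | 17% (17%) | 30% (29%) |
| 1.5 points | 4.57 | 36% (36%) | 57% (58%) |
| 2 points | 8.13 | 61% (62%) | 81% (83%) |

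**Age, other shapes (simulation).**

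| Specificity at 45, 46, 47, 48, 49 (%) | 4-df | Trend |
|---|---|---|
| 89.2, 93.7, 96.2, 93.7, 89.2 | 60% | 8% |
| 94, 94, 85, 94, 94 | 79% | 3% |
| 94, 94, 94, 94, 85 | 79% | 72% |

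**Sparsity by age.** Expected false positives per year are 146.2 x 0.078 = 11.4, and the simulated size of the chi-square test is 5.0%. So there is no problem for specificity. For adenomas, 29/5 = 5.8 cases per year puts every expected cell below 5 at sensitivities of 20 to 50%. Even so, the size is 3.7 to 4.9%, only mildly conservative.

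**Sparsity by race, specificity.** An expected count of 5 false positives needs 5/0.078 = 64.1, so 65 subjects in the group.

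| Assumed mix (%) | Expected false positives | Chi-square size | Exact size |
|---|---|---|---|
| 70/15/8/5/2 | 39.9, 8.6, 4.5, 2.9, 1.2 | 5.1% | not run |
| 82/10/5/2/1 | 46.7, 5.7, 2.9, 1.2, 0.5 | 5.6% | 5.0% |
| 85/10/3/1/0.5/0.5 | 48.4, 5.7, 1.7, 0.5, 0.3, 0.3 | 8.1% | 5.3% |

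**Sparsity by race, adenoma sensitivity.** I simulated 29 cases with random group sizes under these mixes and 83/9/4/2/1/1. The chi-square size is 1.5 to 2.5% at a sensitivity of 40 to 42%, 3.1 to 3.6% at 30%, and about 6% at 20%, so the direction of the error depends on an unknown. Under the three tabulated mixes, the exact (Fisher-Freeman-Halton) test had size 1.9 to 4.7% at sensitivities of 20 to 40%.

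**Adenomas by gender.** With 15 against 14 cases and sensitivity 30 to 40%, Fisher's test has size 2.4 to 2.6%; the uncorrected chi-square has 5.2 to 5.8%.

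**The case against.** The strongest reply is that no decision rests on these tests. The SAP confines hypothesis testing to the primary endpoint and treats other p-values as exploratory, and the success criterion is a single bound for the whole 45 to 49 group. That stands, and it fixes the weight of the point. A reader might infer that the label extension turns on the age test; the documents do not make it do so.

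A reader might also infer that a trend test should replace the general test at no cost. The second table refutes this: against a U-shape or a dip at one middle age the trend test has almost no power. Protocol 12.3 expects no difference even from ages 50 to 59, so nothing in the plan points to a monotone pattern. The case is for adding, not substituting.

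Nor is chi-square unreliable throughout. It holds its size for specificity by age, and for adenomas by gender it is closer to nominal than Fisher's test.

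The planned regression including age and race partly covers the ground. But it is built on polyp size and location, and whether age enters as a linear term is not stated.

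Finally, the protocol says chi-square without naming Pearson or the degrees of freedom, and the squared Cochran-Armitage statistic is itself a 1-df chi-square. With most SAP exploratory endpoints redacted, one can say only that no trend or exact method is visible, not that none was planned.

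**Conclusion.** The point holds as a minor improvement to exploratory analyses. If the age comparison is the unordered test, it gives up roughly 12 percentage points of power for a fall of 1 point per year (17% against 29%) and about 20 for 2 points per year (61% against 82%), assuming equal age groups and a centre of 92.2%. Even the trend test is weak against the smaller gradient.

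For race, the nominal 5% test for specificity rejects about 5 to 8% of the time, and the excess matters only in a strongly skewed mix. For adenoma sensitivity it rejects about 1.5 to 3% of the time at a sensitivity near 40%, and more at lower values. All the race figures rest on assumed mixes.

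The documents do not support reading this as a flaw in the study's main conclusion. The primary endpoint, its alpha and the sample size are untouched.

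**What to change.** Amend the exploratory analysis wording in the SAP as follows:

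- **Age:** keep the general five-group test and add a Cochran-Armitage trend test, or a logistic regression with age as a linear term, stating which one is used.
- **Race/ethnicity:** use Fisher-Freeman-Halton exact p-values when any expected count is below 5.
- **Intervals:** report Clopper-Pearson intervals by age year and by race group. Protocol 12.4 names this method for adenoma sensitivity and for overall specificity, but no visible text plans intervals by year or race, so they must be added explicitly.
- **Gender:** no change is needed.

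The cost is a few sentences of SAP text, with no new data; the methods are available in the planned SAS software. The downsides are one more exploratory p-value, little trend-test power against non-monotone patterns (hence keeping the general test), and conservative exact tests in very small tables. If the redacted endpoints already specify such methods, a cross-reference is enough.
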